12.1. Study Record Retention.....	29
12.2. Protocol Changes	29
12.3. Deviations From Protocol	29
12.4. Team Member Expertise	29
12.5. Record of Revisions to this Document.....	31
13. References	31

Abbreviations & Definitions

Through this document, the following acronyms and terms are used. Terms, when capitalized, carry the specific meanings described below.

ADL:	Activities of Daily Living
AE:	An Adverse Event is defined as any untoward medical occurrence, including deterioration of a pre-existing medical condition in a patient or clinical investigation subject administered a pharmaceutical product/device and which does not necessarily have a causal relationship with this treatment.
AT:	Assistive Technology.
BCVA:	Best Corrected Visual Acuity
CRF:	Case Report Form
CCTV:	Closed-circuit television, which uses a video camera to project a magnified image onto a TV screen. For people with low vision, it can help with reading, viewing photos and other such tasks
CTA:	Clinical Trial Agreement. Legally binding document between the Sponsor and the Institution and the Investigator defining roles, responsibilities, payment, consideration, intellectual property ownership, liability, publication rights, etc.
DEVICE:	eSight Eyewear. A wearable, video based low vision AT device.
eSKILLS PROFICIENCY PROGRAM:	The eSkills program is a structured training program for eSight Eyewear users. It includes various tasks the improve the user's effectiveness with the device. Normally, eSkills is administered by eSight staff by telephone. For the eQUEST study, eSkills will be administered by Site staff.
ETDRS:	Early Treatment Diabetic Retinopathy Study – the worldwide standard for visual acuity testing.
EYECARE PHYSICIAN:	Optometrist or Ophthalmologist at the Study Site.
EXAMINER:	Any staff at the test site who, under the supervision and oversight of the INVESTIGATOR, will administer portions of the protocol and record results in the CRF.
INSTITUTION:	The Low Vision Clinic, Hospital or other location where Eyecare Physicians and low vision rehabilitation specialists are equipped to

eQUEST -- ESIGHT QUALITY OF LIFE AND EFFICACY STUDY

	conduct this study. The Institution shall have a CTA in place with the Study Sponsor.
INVESTIGATOR:	The eyecare physician responsible for oversight of Study activities at the Institution.
LV:	Low vision
MLVAI:	Melbourne Low-Vision ADL Index Test
MN Read Eye Charts:	A continuous text chart designed for normal and low vision at the Minnesota (MN) Laboratory for Low Vision Research
PD:	Pupil Distance. For the purposes of this study, PD means independent left and right pupil distances from nasal center. PD does not mean the distance between the two pupils.
QOL:	Quality of Life
RESEARCH ASSISTANT:	Site associate deemed qualified, and authorized by the Site PI, to carry out portions of the protocol and complete related sections of the CRF. Often the Research Assistant will be the same Site staff person as the Site Administrator.
SAE:	A Serious Adverse Event is defined as any untoward medical occurrence that: 
• Results in death,• Is life-threatening,• Requires inpatient hospitalization or prolongation of existing hospitalization (visit to emergency department without admission to the hospital is not considered hospitalization),• Results in persistent or significant disability/incapacity or• Is a congenital anomaly/birth defect.
SITE ADMINISTRATOR:	Often the Site Administrator will be the same Site staff person as the Research Assistant.
SPONSOR:	eSight Corp.
STUDY:	The research protocol as defined herein.
SUBJECT ID:	A unique number used to identify a Study Subject. This facilitates the provision of study data if necessary amongst different Study Sites, and between the Study Site and the Sponsor, without disclosing breaching the confidentiality of the Subject.
STUDY MANAGER:	Person appointed by eSight to oversee the overall management of the Study, manage data integrity, and the overall Study schedule.

eQUEST -- ESIGHT QUALITY OF LIFE AND EFFICACY STUDY

STUDY SITE: Also, "Site". There are six Study Sites in the eQUEST Study. These are the locations at which the research is being conducted. In all cases, Study Sites have achieved ethics approval to conduct the Study, and informed consent from the Study Subject.

SUBJECT: An individual enlisted as a participant in the eQUEST Study.

THIRD PARTY SURVERYOR: A HIPAA-trained independent third party, trained to administer the VA LV VFQ-48 and eSight-8 Questionnaires by telephone.

VA LV VFQ-48: Visual function questionnaire designed to measure the difficulty a person has performing daily activities

1. Background

eSight Corp., Toronto, Canada (Sponsor), has developed a wearable, electronic low vision aid, “eSight Eyewear” (Device). eSight Eyewear deploys ophthalmic grade video camera and display components, and real-time video modification algorithms to significantly improve the functional visual performance of people with non-correctable, inoperable low vision caused by eye diseases such as but not limited to:

- Macular Degeneration
- Diabetic Retinopathy
- Stargardt’s Disease

Over 100 million people in the developed world have low vision, defined by the World Health Organization as best corrected visual acuity in the better eye of 20:60 or worse². Other factors can also contribute to low vision such as diminished field of view or impaired occipital/cognitive image processing.

In most cases of low vision, individuals will retain sufficient residual visual function that, with the help of Assistive Technology (AT) devices they can still perform various life tasks or Activities of Daily Living (ADLs). The eSight device can help people perform various ADLs such as:

- Reading
- Interacting with others
- Viewing a computer screen
- Orientation and Mobility
- Watching television
- Distance Viewing

[figure not shown]
The mechanism of eSight Eyewear is to stimulate vestigial retinal function through existing retinal photoreceptors (rods and cones), thereby enabling more effective neurological (cortical/occipital) visual processing, helping the brain to extract more usable information from a visual scene. We do not believe eSight Eyewear affects disease progression, nor does it interact with the body’s metabolism or physiology in any way other than through the stimulus described above. eSight Eyewear is a Class-I medical device. The mechanism of

² “The Global Economic Cost of Visual Impairment”, AMD Alliance International, April 2010

physiological/neurological action with the body's natural processes is through visible light (non-harmful intensities and wavelengths) into the eye.

Limited experiments have demonstrated the benefits of eSight Eyewear to certain subjects, and helped to refine inclusion/exclusion criteria in this study. These preliminary results are presented herein.

This study seeks to generate further evidence-based conclusions about the efficacy of eSight Eyewear for various ADLs in the low vision population. Specifically, the study seeks to understand how eSight Eyewear can be used to improve employee productivity and satisfaction in vocational, educational, and home settings.

An initial assessment was performed by the CNIB where 33 individuals of various age, vision and eye pathologies showed improved visual function for both distance and near vision using traditional visual assessment tests (distance acuity and contrast performance) using various image processing algorithms including variable magnification, adjustable contrast, and colour remapping techniques. The CNIB test did not include assessment of the Activities of Daily Living (ADLs) or seek to measure improved functional vision. To date there are ~400 “early-adopter” individuals with low-vision that wear the glasses in their day-to-day lives. Most users self-report high satisfaction with the device however, the technology has not been subject to rigorous scientific study to determine which users would most benefit from using this technology and how the glasses improve their functional visual performance and quality of life. Considering the high cost of this technology (\$15,000) this Clinical Study will guide patients and physicians on the expected benefits and indications for the large population affected with untreatable vision disorders.

1.1. Prior Research

There have been previous attempt to develop and commercialize a head-borne video based low vision aid. The original design from the 90's was called the Low Vision Enhancement System

(LVES), developed by researchers at John Hopkins University³. The LVES device was the subject of various studies and notably, was evaluated extensively by the U.S. Department of Veterans Affairs as an aid suitable for visually impaired veterans.⁴

More recently, the “Joint Optical Reflective Display (Jordy) system was developed by Enhanced Vision Systems, Huntington CA, in collaboration with scientists from the National Aeronautics and Space Administration. The Jordy enjoyed margin commercial success, but has been discontinued⁵.

The use of head worn video as opposed to optical magnification does present exciting possibilities for the partially sighted. Various researchers have sought to understand how video enhancements such as contrast, edge enhancement, overlays, and various other techniques not possible through simple optical magnification or filtering, can be used to enhance functional vision^{6, 7, 8, 9}.

There have been other attempts at head-borne video devices for low vision. Historically, all have suffered from the same drawbacks, largely due to technological implementation at that time. These units were large and cumbersome, with limited field of view, poor camera performance, and unacceptable latency¹⁰. eSight Eyewear, by far the most commercially successful such device to date, overcomes these historical shortcomings through leading edge technology choices and various proprietary design elements.

³ Massof, Rickman, “*Obstacles encountered in the development of the low vision enhancement system*”, Optometry and Vision Science. 1992 Jan;69(1):32-41

⁴ Ballinger, Lalle, Maino, Stelmack, Tallman, Wacker, “*Veterans Affairs Multicenter Low Vision Enhancement System (LVES) study: clinical results. Report 1: effects of manual-focus LVES on visual acuity and contrast sensitivity*”. Optometry. 2000 Dec;71(12):764-74.

⁵ Chang, “*Sleek New Devices Help Low-Vision Patients See*”, NY Times, April 2004

⁶ Peli *et al.*, “*Applications of Augmented Vision Head-Mounted Systems in Vision Rehabilitation*”, Journal of the Society for Information Displays. 2007 Dec; 15(12): 1037–1045.

3.1. Sample Size

Subjects will undergo an initial screen and device demonstration (screening arm) to determine their suitability for an extended trial of the device (extended arm). The target number of subjects for the extended arm is 60 subjects.

Power analysis indicates that in a single tailed test with an alpha level of .05 and a power of .95, the relationship between anticipated effect size and the required sample size is shown in the chart at left. As indicated if we assume an effect size in the range 0.40 – 0.45¹², an appropriate n=60 (ten Study subjects per site).

¹¹ The term “functional visual performance” describes the wearer’s ability to perform various Activities of Daily Living (ADL) with better efficacy and speed than using habitual assistive technology devices. In some cases, because of the hands-free, variable distance, and portable attributes of eSight Eyewear, it is hypothesized that certain ADLs may be possible which were previously impossible or very difficult for certain subjects.

¹² This higher than typical anticipated effect size is an appropriate assumption for this Study design, because of prescriptive inclusion criterion (i.e.: not random population).

About $\frac{1}{3}$ to $\frac{1}{2}$ of subjects who fall into the acuity and visual field inclusion criterion described in Section 3.2 below, demonstrate acute objective improvement and an immediate aptitude with the device. Therefore, we anticipate a total of 150-200 to be enrolled in screening arm of the study, from which 60 will be selected to participate in the extended arm, a three month take-home trial of the device. We expect attrition to be low due to the rigorous screening process for participation.¹³

In addition to a clinician's unit, which incorporates trial lens frames and other unique features for fitting and demonstration, each Site will receive devices for Subjects as they are required. The Site and eSight can, at any time, agree to deploy additional devices to accelerate the collection of data.

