- **Subject’s Unit:** If the subject is deemed a suitable candidate for an extended evaluation period, they will receive a unit with the user interface customized for them, along with their prescription lenses incorporated, if applicable.
- **Materials for In-Clinic ADL Testing:** Telephone book, kitchen ingredients, etc.

10. Analysis

Some of the data gathered through the course of this study is subjective, and will be used by eSight to prioritize ongoing improvements to the device.

The minimum objective data that will be reported is acuity, contrast, reading speed, without eSight Eyewear at the beginning of the trial, and with eSight Eyewear at its conclusion.

Further objective data is the comparison between the initial VFQ, and RAND SF-36 scores, and the change, if any, in score at the conclusion of the study.

Data analysis will be conducted using IBM SPSS Statistics version 22. The data will be pooled from all testing sites by the Study Manager. Before merging of the data, any systematic differences among testing sites will be assessed. Should such differences exist, they will be considered in subsequent analyses.

Repeated measures Analysis of Variance (ANOVA) and t-tests will be used to compare the effect of the eSight devices on all dependent variables that adhere to the assumptions of parametric data analysis (continuous variables, normal distribution etc.). Categorical variables or those who do not adhere to parametric assumptions will be compared using repeated-measures non-parametric techniques (e.g. Friedman Test). Qualitative data will be analyzed using qualitative description (Sandelowski, 2000).

³⁸ Requires 22” monitor with HDMI input. To be provided by eSight in the event that the study location does not have one available.

The eSight device contains an electronic logging capability, wherein daily on-time hours, and user commands (e.g.: zoom in/out, focus distance, increase/decrease contrast, etc.) are saved to an SD card. No images or video or other information that may personally identify the subject is recorded. These electronic logs may be used to validate user reported usage data³⁹.

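### With 60 subjects, one-tailed power .95 holds only from an effect size of about 0.43, and the one-tailed calculation does not cover the non-directional tests named in Section 10

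*Combined protocol and SAP*

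**What the plan says.** Section 3.1 (Sample Size) gives the plan's only power statement. It begins: "Power analysis indicates that in a single tailed test with an alpha level of .05 and a power of .95". The effect size enters as "if we assume an effect size in the range 0.40" to 0.45, and the section concludes with "an appropriate n=60 (ten Study subjects per site". The relation between effect size and sample size is said to be in a chart, which is not in the readable text. The metric of the effect size is not named there.

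On loss to follow-up, Section 3.1 says "We expect attrition to be low due to the rigorous screening process for participation". It gives no rate and does not inflate the 60. Section 5 allows withdrawn subjects to be replaced, but only if time allows.

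Section 10 (Analysis) describes the tests: "Repeated measures Analysis of Variance (ANOVA) and t-tests will be used to compare the effect of the eSight devices on all dependent variables" that meet parametric assumptions. For the others it plans repeated-measures non-parametric techniques, with the Friedman test as the example. For the VFQ and SF-36 it compares initial scores with "the change, if any, in score at the conclusion of the study". It gives no alpha level and no tail for any test.

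**The concern.** Two things do not fit. First, a sample size justified for a range of effects should hold at the low end of that range, where it is hardest to meet. The smallest effect the plan allows for is 0.40, so the .95 should be checked there.

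Second, the power figure is one-tailed, while two of the three kinds of test in Section 10 (repeated-measures ANOVA and Friedman-type tests) have no direction. The third, the t-test, is listed without a tail. The power figure and the planned tests may therefore describe different procedures.

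At stake is how a null result is read. A reader who takes Section 3.1 at face value will set it against a 5% chance of missing a true effect of the assumed size. The tail also decides what can be concluded: a one-tailed test for improvement cannot declare a worsening, such as slower reading with the device.

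**Working it through.** **Inputs.** Alpha .05, one-tailed, power .95, effect size d = 0.40 to 0.45 and n = 60 come from Section 3.1. The within-subject comparison, without the device at the start and with it at the end, comes from Section 10. Assumption: d is the mean paired change divided by the standard deviation of the paired changes.

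**Formulas.** For a paired t-test, power comes from the noncentral t distribution with df = n − 1 and noncentrality d × √n. With n = 60, √60 = 7.746, so the noncentrality is 0.40 × 7.746 = 3.10 at the low end and 0.45 × 7.746 = 3.49 at the high end. The normal approximation to the required size is n = ((z for alpha + z for power) / d)².

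**The plan's own figure.** One-tailed, both z values are 1.645. At mid-range, d = 0.425, n = (3.290 / 0.425)² = 59.9, or 60. The exact t calculation gives 62. So 60 reproduces near the middle of the range on the plan's one-tailed basis. At the ends the approximation gives 68 and 54.

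**Exact noncentral-t results.**

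| d | One-tailed power, n = 60 | One-tailed n for .95 | Two-sided power, n = 60 | Two-sided n for .95 |
|---|---|---|---|---|
| 0.40 | 0.922 | 70 | 0.862 | 84 |
| 0.425 | 0.946 | 62 | 0.899 | 74 |
| 0.43 | 0.950 | 60 | 0.906 | 73 |
| 0.45 | 0.964 | 55 | 0.929 | 67 |

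The smallest d with power .95 at n = 60 is 0.430 one-tailed and 0.473 two-sided. The second value lies above the plan's range. A repeated-measures ANOVA with two levels is the same test as the two-sided paired t, so the two-sided columns apply to it.

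**Miss rates with 60 analysed.** One-tailed: 1 − 0.964 = 3.6% to 1 − 0.922 = 7.8%. Two-sided: 1 − 0.929 = 7.1% to 1 − 0.862 = 13.8%.

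**Loss, for illustration only.** The documents give no dropout rate. If 54 completed (10% of 60 lost and not replaced), power across the range would be 0.896 to 0.947 one-tailed and 0.823 to 0.901 two-sided.

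**Other readings of the effect size.**
- A correlation: the one-tailed n is about 63 at 0.40 and 49 at 0.45, so 60 again falls short at the low end.
- Two independent groups: 136 per arm at 0.40 and 107 at 0.45, one-tailed. This fits neither the figure of 60 nor the single-group design.
- Cohen's f in a repeated-measures ANOVA with two or three levels: power at n = 60 is 0.99 or more, even with zero correlation between occasions.

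**The case against.** The strongest reply is that Section 3.1 does not claim .95 at 0.40. It claims that 60 suits a range, and 60 lies within the 55 to 70 that the range implies one-tailed. This stands in part. A reader might infer that the stated power is simply wrong, but the figure reproduces near mid-range and is met from about 0.43 upward. What remains is a shortfall of 2.8 points at 0.40.

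The second reply is that Section 10 never says its tests are two-sided. That also stands. The t-tests could be one-tailed as in Section 3.1, and footnote 11 defines functional visual performance in a favourable direction, which suits a one-tailed test. Section 10's wording about change in the VFQ and SF-36 is ordinary description, not a two-sided hypothesis. A reader might infer that the plan prescribes two-sided tests throughout, and the documents do not support that. They do support a narrower point: the tail is omitted, and the ANOVA and Friedman-type tests fall outside a one-tailed calculation.

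The third reply is that the result depends on an unnamed metric and an unseen chart. This is a real limit. Under Cohen's f, power would exceed .95. But f belongs to an F-test, which has no tail, and 60 would then be far more than .95 requires, so that reading fits Section 3.1 poorly. Nor is every possible ANOVA below .95. With three levels, f = d/2 and a correlation of 0.5 (all assumptions), power is 0.929 at 0.40 and 0.973 at 0.45.

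Finally, a reader might infer a true miss rate as high as 18%. That figure needs a two-sided test, d = 0.40 and 54 completers together, and the 10% loss is not in the documents. Section 3.1 expects low attrition, and Section 5 allows some replacement.

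**Conclusion.** The point holds in a limited form. If the effect size is the standardised mean paired change, 60 analysed subjects give one-tailed power of 0.92 to 0.96 across the plan's range, with .95 only from about 0.43. For a two-level repeated-measures ANOVA or a two-sided paired t-test, power is 0.86 to 0.93 and never reaches .95 within the range. Any loss that is not replaced lowers these figures.

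The stated .95 is thus correct for part of the range under one tail, and it does not carry over to the non-directional tests that Section 10 names. Nothing here shows that 60 is too few: with 60 analysed, every paired-test figure above exceeds 0.80. The fault is that the plan's only power figure does not match its own range and tests. It is worth correcting because the correction is cheap and the figure will be used to interpret null results.

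**What to change.** Keep 60. In Section 3.1, name the effect-size metric. Then make the tail in Section 3.1 agree with the tests in Section 10, by one of two routes:

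- **Two-sided.** State in Section 10 that start-to-end comparisons are two-sided paired tests at .05. Restate power in Section 3.1 as 0.86 at an effect size of 0.40 and 0.93 at 0.45, with 60 completers.
- **One-tailed.** State the direction for each outcome in Section 10 and use directional paired tests for those comparisons. Restate power as 0.92 to 0.96, noting that .95 is reached only from about 0.43 and with no dropout.

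Both sets of figures assume the standardised mean paired change. If the sponsor used another metric, the power should be recomputed on it.

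The cost is a few sentences in Sections 3.1 and 10 and a less favourable stated power. No extra subjects, visits or measurements are needed.

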3.2. Inclusion Criteria

1. Male or female subjects between the ages of 13-75. The goal for the extended arm is that 50% of subjects will be 65 years of age or younger, and 50% will be older than 65¹⁴.
2. Subject must have distance BCVA measured with ETDRS of between 20:60 and 20:400 in the better eye.
3. Subjects have been diagnosed with a condition that presents as one or all of the following: Central scotomata, geographic atrophy, or scattered scotomata. These are typically symptoms attributed to conditions such as: Diabetic Retinopathy, Stargardt's Disease, Age Related Macular Degeneration, Leber's Disease, Retinopathy of Prematurity, Cone Rod Dystrophy, or Ocular Albinism¹⁵.
4. Subject must have an estimated functional field of view of at least 20 degrees (bilateral or monocular).¹⁶
5. If the subject is employed, they must be prepared to use eSight Eyewear in their workplace environment, have informed their employer of their involvement in the study, and received permission from their employer to bring eSight Eyewear into the workplace. If the subject is self-employed, they must be prepared to use eSight Eyewear in their

¹³ "Sample size estimation and power analysis for clinical research studies", Suresh & Chandrashekar, J Hum Reprod Sci. 2012 Jan-Apr; 5(1): 7-13. "G*Power 3: a flexible statistical power analysis program for the social, behavioral, and biomedical sciences", Erdfelder, Faul, & Buchner, Behav Res Methods. 2007 May;39(2):175-91.

¹⁴ The intention of this stratification of the cohort is to understand age effects related to the eSight Eyewear device. This stratification does not impact the statistical analysis in Section 3.1

¹⁵ These have been demonstrated by current eSight users to be conditions for which eSight Eyewear can provide significant benefit. For other conditions, especially those which present as peripheral degeneration encroaching inwardly ultimately towards the central vision, eSight Eyewear's effectiveness has not yet been convincingly demonstrated (e.g.: early stage Retinitis Pigmentosa, early stage Glaucoma).

¹⁶ Acuity and field criteria, while firm requirements here, are inflection points in the real world population. Evidence indicates that eSight users outside of the 20/60 – 20/400 BCVA and 20° field can still have success with the eSight device, but results are less consistent.

workplace environment. Similarly if the subject is a student, they must be prepared to use eSight Eyewear in their educational environment.

[figure not shown]
6. Subject must be, in the opinion of the examiner, highly motivated, alert, articulate, mentally competent and able to understand and comply with the requirements of the study (defined herein).
7. Subject must provide informed consent. Subjects under the age of majority must have a legal guardian present during the informed consent process, who must sign the Informed Consent form on their behalf.
8. Subject must agree to use eSight Eyewear only under conditions that will not jeopardize the safety of either the user or the device.

